6.4 Hepatotoxicity Stopping and Rechallenge Rules

Subjects with abnormal hepatic laboratory values (ie, ALP, AST, ALT, total bilirubin [TBL]) and/or international normalized ratio (INR) and/or signs/symptoms of hepatitis (as described below) may meet the criteria for withholding or permanent discontinuation of Amgen IP or other protocol-required therapies (as specified in the Guidance for Industry Drug-Induced Liver Injury: Premarketing Clinical Evaluation, July 2009). **Note: If the central laboratory is unable to perform the analysis of the hepatic laboratory tests (as discussed with Amgen during screening) then those tests should be measured by the local laboratory.**

6.4.1 Criteria for Permanent Discontinuation of Amgen Investigational Product and Other Protocol-required Therapies due to Potential Hepatotoxicity

IP should be discontinued permanently by the Investigator and the subject should be followed according to the recommendations in [Appendix A](#) (Additional Safety Assessment Information) for possible drug-induced liver injury (DILI), if ALL of the criteria below are met.

- TBL > 2 x ULN or International Normalized Ratio (INR) > 1.5
- AND increased AST or ALT from the relevant baseline value as specified below:

Baseline AST or ALT value	AST or ALT elevation
< ULN	> 3x ULN

- **AND no other cause for the combination of laboratory abnormalities is immediately apparent; important potential causes for abnormal AST/ALT or TBL values include, but are not limited to:**
 - Obstructive gall bladder or bile duct disease
 - Viral or alcoholic hepatitis (eg, Hepatitis A/B/C/D/E, Epstein-Barr Virus, cytomegalovirus, Herpes Simplex Virus, Varicella, etc)
 - Hypoxic or ischemic hepatopathy or congestive hepatopathy in association with significant right sided heart failure
 - Concomitant administration of other hepatotoxins, including drugs that inhibit bilirubin glucuronidation (eg, indinavir, atazanavir, irinotecan) or herbal or dietary supplements
 - Heritable disorders causing impaired glucuronidation (eg, Gilbert's Syndrome); alpha-one antitrypsin deficiency
 - Autoimmune hepatitis
 - Nonalcoholic Steatohepatitis (NASH) or other “fatty liver disease”

If an alternative cause for hepatotoxicity is identified or less stringent conditions developed than what are noted above, determine (based on subject population and/or

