7.1 Schedule of Assessments

Table 2. Schedule of Assessments

Study Week	Screening	Treatment Period ^a																
		Day 1	2	3	4	5	6	7	8	9	10	11	12	13	14	15	16	17
Study Day	Day -56 to -1	Day 1	8-14	15-21	22-28	29-35	36-42	43-49	50-56	57-63	64-70	71-77	78-84	85-91	92-98	99-105	106-112	113-119
IV investigational product administration		Three times per week at the end of the hemodialysis session starting from day 1																
Dose titration ^b						X				X					X			X
Informed Consent	X																	
Inclusion/Exclusion	X																	
Medical History	X																	
Demographics	X																	
Prior & Concomitant Medication	X	X	X	X	X	X	X	X	X	X	X	X	X	X	X	X	X	X
Physical Examination	X																	
Assessment of Kt/V or URR ^{IL}	X																	
Randomization ^c		X																
Dispensation of oral IP bottle		X			X			X		X		X		X		X		X
Pill count			X		X		X		X		X		X		X		X	
TIW Admin of IV IP (by site staff at the end of hemodialysis) ^d		X	X	X	X	X	X	X	X	X	X	X	X	X	X	X	X	X
Adverse events ^e	X	X	X	X	X	X	X	X	X	X	X	X	X	X	X	X	X	X
Prior to dialysis																		
ECG ^f	X																	
Serum pregnancy test ^g	X	X												X				
Hematology	X																	
Chemistry	X																	
Albumin, Ca ^{ij}		X	X		X		X		X		X		X		X		X	
Phosphorus		X			X				X				X				X	
PTH	X	X	X		X		X		X		X		X		X		X	
PK ^h					X									X				
25(OH)D		X																
ADA			X										X					

Page 1 of 2

Footnotes defined on the next page

Approved

Schedule of Assessments

Table 2. Schedule of Assessments

Study Week	Screening	Treatment Period ^a																
		Day 1	2	3	4	5	6	7	8	9	10	11	12	13	14	15	16	17
Study Day	Day -56 to -1	Day 1	8-14	15-21	22-28	29-35	36-42	43-49	50-56	57-63	64-70	71-77	78-84	85-91	92-98	99-105	106-112	113-119
After dialysis																		
Pulse and blood pressure ^{ik}		X																
Height		X																
Weight		X																
PK (10-30 minutes postdose) ^h					X									X				

Page 2 of 2

25(OH)D = 25-hydroxy vitamin D; ADA = antidrug antibody; [REDACTED]; cCa = correct calcium; Ca = calcium; [REDACTED];

ECG = electrocardiogram; IP = investigational product; HIV = Human immunodeficiency virus, IV = intravenous; Kt/V = measure of dialysis adequacy;

PTH = parathyroid hormone, PK = pharmacokinetic;

TIW = three times per week; URR = urea reduction ratio

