	18	19	20	21	22	23	24	25	26	27 ^b			
IV investigational product administration				Three times per week at the end of the hemodialysis session ending at week 26									
Dose titration ^c													
Informed Consent													
Inclusion/ Exclusion													
Medical History													
Demographics													
Prior & Concomitant Medication	X	X	X	X	X	X	X	X	X	X	X	X	
Physical Examination											X	X	
Randomization													
Dispensation of oral IP bottle				X				X					
Pill count	X		X		X		X	X	X			X	
TIW Admin of IV IP (by site staff at the end of hemodialysis) ^d	X	X	X	X	X	X	X	X	X				
Adverse events ^e	X	X	X	X	X	X	X	X	X	X	X	X	
Vital status ^f									X			X	
Prior to dialysis													
ECG ^g										X		X	
Serum pregnancy test ^h						X					X	X	
Hematology											X	X	
Chemistry											X	X	
Albumin, Ca ^{ij}	X		X		X		X		X	X			X ^d
Phosphorus			X			X		X	X				
PTH	X	X	X		X		X		X	X	X	X	
PK ^k								X		X			
25(OH)D													
ADA											X	X	
After dialysis													
Pulse and blood pressure ^L									X			X	
Height													
Weight									X			X	
PK (10-30 min post dose) ^{ik}							X						

Footnotes defined on the next page

Approved

ADA = antidrug antibody; [REDACTED]; cCa = correct calcium; Ca = calcium; [REDACTED]; ECG = electrocardiogram;

IP = investigational product; IV = intravenous; PTH = parathyroid hormone, PK = pharmacokinetic; TIW = three times per week

^a Assessments during the Treatment Period should be performed during the designated study week on the same hemodialysis treatment day of the week as the day dosing was started whenever possible.

^b Week 27 assessments should be performed on the day of the first hemodialysis treatment after the last dose of IP.

^c The dose of IP may be decreased at any time.

^d When dosing with IP is suspended for cCa < 7.5 mg/dL (**1.87 mmol87mmol/L**), a predialysis serum sample for albumin and calcium should be submitted to the central laboratory on the day dosing is suspended. Dose suspension samples do not need to be collected if a routine, local chemistry or albumin/calcium/P sample is obtained on the same day.

^e After informed consent and before first dose of IP, only serious adverse events are to be reported. Subjects will be followed for both adverse events and serious adverse events for 30 days after the last dose of IP.

^f Vital status will only be appropriately ascertained by sites for subjects who early terminated the study.

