7.2.4 Follow-up Visit

Subjects will complete the follow-up visit 30 days (\pm 3 days) after the last dose of IP. If a subject early terminates from IP or the study, the follow-up visit should also occur within 30 days (\pm 3 days) after the last dose of IP.

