7.2.5 Early Termination of Investigational Product Visit

Subjects discontinuing IP prior to week 26 should return to the site for an early termination (ET) visit (refer to [Table 2](#) and [Table 3](#) for ET assessments) at the first hemodialysis treatment after the last dose of IP if at all possible, or at the earliest possible hemodialysis treatment. Additionally, every attempt should be made to complete a follow-up visit 30 days (\pm 3 days) from the last dose of IP.

After discontinuing IP, the subject may continue to participate in the study with varying levels of follow-up (refer to [Section 8.1](#)).

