7.4 Laboratory Assessments

All screening (except URR) and on-study laboratory samples will be processed and sent to the central laboratory. If screening samples for URR or Kt/V are required, they will be processed at the site's local laboratory. When dosing with IP is suspended for $c\text{Ca} < 7.5 \text{ mg/dL (1.87 mmol/L)}$, a predialysis serum sample for albumin and calcium should be submitted to the central laboratory on the day dosing is suspended. Dose suspension samples do not need to be collected if a routine, local chemistry or albumin/calcium/phosphorous sample is obtained on the same day. The results of this testing will be maintained in the source documents at the site. The central laboratory will provide a study manual that outlines handling, labeling, and shipping procedures for all samples. Please refer to the central laboratory manual for the complete listing of analytes run by the central laboratory. Blood samples will be obtained before IP administration (except for the post-dialysis PK samples). The date and time of sample collection will be recorded in the source documents at the site.

[Table 4](#). outlines the specific analytes for serum chemistry, hematology, urinalysis, and other testing to be conducted on blood and urine samples by central, local, or core laboratories.

Approved

Table 4. Analytes Table

Chemistry	Hematology ^c	Other
Sodium	Hemoglobin	Antibodies ^a
Potassium	Hematocrit	Pregnancy test
Chloride	Platelets	Intact PTH
Bicarbonate	WBC	25-hydroxyvitamin D
Total protein	RBC	
Albumin		
Calcium		Urea ^b
Corrected calcium (calculated)		
Magnesium		
Phosphorus		
Glucose		
Total bilirubin ^c		
Direct bilirubin ^c		
ALP		
LDH		
AST (SGOT) ^c		
ALT (SGPT) ^c		

ALP = serum alkaline phosphatase; ALT = alanine aminotransaminase; AST = aspartate transaminase;

[REDACTED]; LDH = lactate dehydrogenase;

PTH = parathyroid hormone; RBC = red blood cells; SGOT = Serum glutamic oxaloacetic transaminase;
SGPT = Serum glutamic pyruvic transaminase; WBC = white blood cells

^aThese assays may be performed at a specialty laboratory

^bUrea measurement to be performed locally for Kt/V or URR assessment at screening, unless a qualifying Kt/V or URR measurement from within 4 weeks prior to screening assessments is available.

^cIf the central laboratory result is not available, local laboratory values may be used to determine eligibility, but Amgen must be contacted prior to randomization.

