### Follow-up

The 30-day period that occurs after a subject receives the last dose of investigational product during which safety information will be collected.

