### **9.6.3 Laboratory Test Results**

Laboratory values below the parameter-specific the lower limit of quantification (LLOQ) or above the parameter-specific upper limit of quantification (ULOQ) will be imputed as the LLOQ or ULOQ value, respectively.

In this section, cCa refers to cCa measured by central laboratory, Ca refers to Ca measured by central laboratory. All cCa and Ca results from local laboratory testing will be excluded from analysis.

Laboratory parameters including corrected calcium, PTH, P and Ca x P will be summarized by treatment group and the protocol-specified scheduled visit. Summaries of the absolute value change from baseline, and percent change from baseline will also be provided.

Shift tables will be provided for albumin, corrected calcium, potassium, phosphorus, magnesium, hemoglobin, alkaline phosphatase (ALP), alanine aminotransferase (ALT), aspartate aminotransferase (AST), total bilirubin (TBL) by summarizing the most

---

extreme changes in toxicity grade from baseline (increase and/or decrease as appropriate) to any visit during the study while the subjects are receiving IP. The toxicity grading will be based on common terminology criteria for adverse events (CTCAE) version 4.0.

Number and percentage (with 95% confidence interval) of subjects with low calcium as defined by cCa < 7.0 mg/dL, < 7.5 mg/dL, < 8.0 mg/dL, < 8.3 mg/dL, 7.0 - < 7.5 mg/dL, and 7.5 - < 8.3 mg/dL during the study will be summarized by treatment group. Each subject's lowest corrected calcium value during the study (post-baseline) will be used in this analysis.

Number and percentage of subjects with 2 consecutively low corrected calcium, defined by 2 consecutive post-baseline corrected calcium < 7.5 mg/dL, < 8.0 mg/dL and < 8.3 mg/dL during the study will be summarized by treatment group.

A summary of potential Hy's law cases meeting lab criteria will be provided. Subject incidence meeting the following criteria will be provided at baseline and post-baseline:

ALT or AST > 3 x ULN and TBL  $\geq$  2 x ULN and ALP < 2 x ULN within  $\pm$  7 days  
For subjects who meet the Hy's law lab criteria, information on their medical history and concomitant medication will be provided to further evaluate whether these are true Hy's law cases.

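### The on-IP window for the CTCAE shift tables leaves seven of the ten listed analytes with no scheduled post-baseline value

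*SAP*

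**What the plan says.** SAP 9.6.3 lists ten analytes for shift tables: albumin, corrected calcium, potassium, phosphorus, magnesium, hemoglobin, ALP, ALT, AST and total bilirubin (TBL). The comparison runs from baseline "to any visit during the study while the subjects are receiving IP". For analytes other than PTH, corrected calcium and phosphorus, SAP 5.2 takes the last non-missing value up to Study Day 1 as baseline. For the full panels that is the screening sample.

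Protocol 7.1 sets the dosing period. Table 2 shows IV product given "Three times per week at the end of the hemodialysis session starting from day 1", and Table 3 shows it "Three times per week at the end of the hemodialysis session ending at week 26". The Chemistry and Hematology rows are marked only at screening in Table 2, and only in the follow-up and early termination columns in Table 3.

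Both post-baseline visits are tied to the last dose:

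- Protocol 7.2.4: "Subjects will complete the follow-up visit 30 days" (± 3 days) after it.
- Protocol 7.2.5: early termination is "at the first hemodialysis treatment after the last dose of IP if at all possible".
- SAP 5.1 defines follow-up as "The 30-day period that occurs after a subject receives the last dose of investigational product".

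**The concern.** The analysis window and the sampling schedule do not meet for the full-panel analytes. They have a baseline, but nothing is scheduled on treatment to shift to. What could enter is unscheduled: magnesium checked in subjects with hypocalcemia (protocol 6.2.3.3), or repeat liver tests (Appendix A). Such values come from subjects who already had a reason to be tested.

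The protocol synopsis commits to analyzing hematology and chemistry, and the shift tables are the only summary in SAP 9.6.3 that names potassium, magnesium or hemoglobin. An empty or nearly empty table could be misread as an absence of shifts. Meanwhile the panel that every completer is due to give at follow-up would be left out of these tables.

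**Working it through.** The documents give no figure to reproduce here, so the check is a count of scheduled samples.

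**Step 1: map analytes to schedule rows.** The panels come from protocol Table 4, the visit marks from Tables 2 and 3. On-IP visits are weeks 2 to 26. Week 27 is excluded because its footnote places it at the first hemodialysis after the last dose.

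| Analyte | Schedule row | Scheduled on-IP draws after day 1 |
|---|---|---|
| Albumin | Albumin, Ca | 13 |
| Corrected calcium | Albumin, Ca | 13 |
| Phosphorus | Phosphorus | at least 4 |
| Potassium, magnesium, ALP, ALT, AST, TBL | Chemistry | 0 each |
| Hemoglobin | Hematology | 0 |

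- Albumin and calcium: weeks 2, 4, 6, 8, 10, 12, 14, 16 (8 draws, Table 2) plus weeks 18, 20, 22, 24, 26 (5 draws, Table 3); 8 + 5 = 13.
- Phosphorus: weeks 4, 8, 12, 16 in Table 2 = 4. The Table 3 marks may have moved in text extraction, so they are not relied on.
- The schedule footnote saying that chemistry also includes albumin and calcium does not turn the two-weekly albumin/calcium draw into a full panel.

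**Step 2: count analytes with nothing in the window.** 6 (chemistry) + 1 (hemoglobin) = 7; 7/10 = 70%.

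**Step 3: what the rule discards.** A completer has one scheduled post-baseline panel, at 30 − 3 = 27 to 30 + 3 = 33 days after the last dose. It carries one value for each of the seven analytes, and the window keeps 0 of 7. A subject who stops early has up to two panels (early termination and follow-up), both after the last dose.

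**Step 4: is the count an artefact of broken columns?** The Physical Examination row of Table 3 has the same two marks, and protocol 7.3.4 confirms them by naming the 30-day follow-up and early termination visits. Even if the Chemistry and Hematology marks belonged one column to the left, the first would fall at week 27, still after the last dose.

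**Step 5: local results.** SAP 9.6.3 excludes local results only for corrected calcium and calcium. Table 4 note c, attached to hematology, bilirubin, AST and ALT, says that if "the central laboratory result is not available, local laboratory values may be used to determine eligibility". Protocol 6.4, which covers ALP, AST, ALT and TBL, sends tests to the local laboratory "If the central laboratory is unable to perform the analysis of the hepatic laboratory tests". So local values are possible in some circumstances for 5 of the 7: hemoglobin, ALP, ALT, AST and TBL. For hemoglobin the allowance concerns eligibility only, so it bears on baseline.

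**The case against.** The strongest reply is that the on-IP limit has no stated lag. The early termination panel is drawn at about the time the next dose would have been due, and a common on-treatment convention would count it. If the 10% dropout in the sample size section applied and every such subject attended that visit (both assumptions), up to 0.10 × 660 = 66 subjects would contribute a value. This stands as a possible reading, but the SAP text gives no lag, and completers would still have none.

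The limit to any visit can also be read to admit unscheduled values, so the tables need not be literally empty. That is true, but the values would be cause-driven. SAP 5.3 uses unscheduled results to replace missing scheduled ones, and here there is no scheduled on-IP visit to replace.

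Other safeguards reduce the harm:

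- The by-visit laboratory summary is worded non-exclusively and could cover these analytes, although it names only corrected calcium, PTH, P and Ca x P.
- Laboratory changes that need treatment become adverse events (protocol 9.2.1.1).
- The Hy's law summary uses post-baseline values without the on-IP limit.

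These points stand, and they confine the problem to the shift tables.

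Finally, limiting toxicity shifts to on-drug values is a legitimate choice in principle. It works only where on-drug samples are scheduled. Some SAP appendix pages are not in the public copy, so a laboratory window defined there cannot be ruled out; nothing in the visible text points to one.

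**Conclusion.** The concern holds. As written, seven of the ten shift tables have no scheduled post-baseline value in their window, while those for albumin, corrected calcium and phosphorus work as intended. The rule does not fit the schedule, so following it exactly gives seven tables that are empty or selectively filled.

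The consequence is descriptive: no named endpoint or formal test changes. The SAP should be corrected, but the trial's conclusions on efficacy do not depend on it. The verdict assumes that receiving IP ends at the last dose and that the Chemistry and Hematology rows are read as in Step 1. Step 4 shows that the count survives a one-column shift.

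**What to change.** In SAP 9.6.3:

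1. Keep the on-IP limit for albumin, corrected calcium and phosphorus.
2. For potassium, magnesium, hemoglobin, ALP, ALT, AST and TBL, write: *most extreme grade from first dose through the 30-day follow-up visit, including early termination and unscheduled values*.
3. State whether local-laboratory values of hemoglobin, ALP, ALT, AST and TBL count, at baseline and after it.
4. Add a footnote: *Scheduled post-baseline values for these analytes are obtained after the last dose of IP (27-33 days after for completers)*.

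A second window has precedent: 9.6.3 already uses all post-baseline values for the lowest corrected calcium. The treatment-emergent adverse event window in SAP 5.3 is close but not identical. It stops 30 days after the last dose, so a follow-up sample on days 31 to 33 would fall outside it.

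The cost is one window sentence, one sentence on local values and one footnote, with no new samples. The downside is that off-drug values enter seven tables and may miss or dilute on-drug changes, and the ten tables no longer share one window. With the sampling schedule unchanged, the tables still cannot show routine on-drug values for these analytes, which is why the footnote is needed.

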#### **9.6.4            Vital Signs**

Vital signs will be summarized by treatment group at each protocol-specified time point.

#### **9.6.5            Physical Measurements**

Physical measurements will be summarized by treatment group at each protocol-specified time point.

#### **9.6.6            Electrocardiogram**

The electrocardiogram (ECG) measurements from this clinical study were performed as per standard of care for routine safety monitoring, rather than for purposes of assessment of potential QT interval corrected (QTc) effect. Because these evaluations may not necessarily be performed under the rigorous conditions expected to lead to meaningful evaluation of QTc data; neither summaries nor statistical analyses will be provided, and these data would not be expected to be useful for meta-analysis with data from other trials.

#### **9.6.7            Antibody Formation**

The incidence and percentage of subjects who develop anti-etelcalcetide antibodies at any time, at baseline and post baseline will be tabulated for the etelcalcetide arm.

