1.3 Safety

- Assess the safety and tolerability of etelcalcetide compared to cinacalcet
- Evaluation of antibody formation to etelcalcetide

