^a Baseline assessments will be performed on the first day of dosing with IP (day 1). Assessments during the Treatment Period should be performed during the designated study week on the same hemodialysis treatment day of the week as the day dosing was started whenever possible.

^b The dose of IP may be increased or decreased at any time. The dose of either active IP will be titrated to target predialysis [REDACTED] but maintaining cCa \geq 8.3 mg/dL (**2.07 mmol/L**). Doses of investigational product will be managed by IVR/IWR and will be based on regular measurements of serum PTH and cCa levels obtained the week before dose adjustment.

^c The first dose of IP should occur within 1 day after randomization.

^d When dosing with IP is suspended for cCa $<$ 7.5 mg/dL (**1.87 mmol/L**), a predialysis serum sample for albumin and calcium should be submitted to the central laboratory on the day dosing is suspended. Dose suspension samples do not need to be collected if a routine, local chemistry or albumin/calcium/P sample is obtained on the same day.

^e After informed consent and before first dose of IP, only serious adverse events are to be reported. Subjects will be followed for both adverse events and serious adverse events for 30 days after the last dose of IP.

^f Subjects should remain supine or sitting for at least 10 minutes prior to recording the screening ECG, and be supine during the ECG. The screening predialysis ECG is a single recording.

^g Additional pregnancy tests may be performed at the discretion of the investigator or per local regulatory requirements.

^h PK assessments can be done at any hemodialysis session during the treatment week. **Note: Per Section 7.4.2 this will not be drawn in subjects with a known history of HIV.**

ⁱ To be measured by the central laboratory

^j Chemistry will also include albumin and calcium

^k Subjects must be in a supine position in a rested and calm state for at least 5 minutes prior to all measurements of pulse rate and blood pressure. If the subject is unable to be in the supine position, the subject should be in most recumbent position as possible.

^l Perform Kt/V or URR assessment at screening unless a qualifying Kt/V or URR measurement from within 4 weeks prior to screening assessments is available.

Table 3 Schedule of Assessments Continued

Study Week (Study Day)	Treatment Period ^a										Follow-up 30 days after last dose ± 3 days	Early Term	Dose Suspension

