7.2.3 Treatment

Procedures will be completed during the 26-week treatment period at the times designated in the Schedule of Assessments ([Table 2](#)). Prior to enrollment, subject eligibility must be confirmed with screening procedures. Subjects satisfying eligibility requirements will be enrolled and randomized 1:1 to either etelcalcetide or cinacalcet into the 26 week treatment period and should receive the first dose of investigational product within 1 day of randomization. Randomization will be stratified by screening PTH level (< 900 pg/mL, \geq 900 pg/mL) (**< 95.40 pmol/L, \geq 95.40 pmol/L**), screening **central laboratory** serum cCa (\geq 9.0 mg/dL, < 9.0 mg/dL) (**\geq 2.25 mmol/L, < 2.25 mmol/L**) measured by the central laboratory, and country (China versus

non-China). The date of the first dose of IP is defined as day 1. Baseline assessments will be performed on the first day of dosing with IP (day 1). All subsequent study visits will be scheduled based on the day 1 date.

The IP is to be administered after all pre-dose assessments have been completed on day 1. Administration of IV IP is to be administered 3 times per week at the end of each hemodialysis session as specified in [Section 6.2.1](#). Assessments during the Treatment Period should be performed during the designated study week on the same hemodialysis treatment day of the week as the day dosing was started whenever possible. Oral IP should be taken by the subject with food at approximately the same time every day of the 26-week treatment period as described in [Section 6.2.2](#). Week 27 assessments should be performed on the day of the first hemodialysis treatment after the last dose of IP. Concomitant medications, adverse events, and serious adverse events must be collected at every study visit.

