7.4.1 Hepatitis Testing

Baseline hepatitis testing may be conducted if there is a clinically relevant increase in liver function tests of unknown etiology during the study or the increase meets the criteria for permanent discontinuation or conditional withholding of Amgen IP because of potential hepatotoxicity. For this purpose, a baseline sample will not be specifically stored for hepatitis testing but will be taken from the back-up baseline sample for

antibody testing. If needed, a hepatitis-screening panel (for hepatitis A, B, and C) will be performed.

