10.1.1.4 Safety Endpoints

- Incidence of cCa $<$ 8.3 mg/dL **measured by the central laboratory** at any time during the study
- Incidence of cCa $<$ 8.0 mg/dL **measured by the central laboratory** at any time during the study
- Incidence of cCa $<$ 7.5 mg/dL **measured by the central laboratory** at any time during the study
- Incidence of treatment-emergent symptomatic hypocalcemia during the study
- Incidence of antibody formation to etelcalcetide
- Nature, frequency, severity, and relationship of treatment-emergent adverse events.

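### Table 2, as extracted, shows no antibody sample before dosing, yet protocol 7.4.1 and SAP 9.6.7 both depend on a baseline antibody sample

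*SAP*

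**What the plan says.** Antibody formation is a named safety objective (protocol 1.3: "Evaluation of antibody formation to etelcalcetide") and a named safety endpoint (protocol 10.1.1.4: "Incidence of antibody formation to etelcalcetide").

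Four places bear on when the samples are taken:

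- **Protocol 7.1, Table 2.** Read by column, the ADA row has marks at Week 2 and Week 12, and none at Screening or Day 1. IV dosing in the same table runs "Three times per week at the end of the hemodialysis session starting from day 1". Table 3 adds ADA marks at the follow-up and early termination visits.
- **Protocol 7.5.** It describes antibody testing, allows extra samples and exempts subjects with known HIV, but names no visit.
- **Protocol 7.4.1.** If hepatitis testing at baseline is needed later, "a baseline sample will not be specifically stored for hepatitis testing but will be taken from the back-up baseline sample" kept for antibody testing.
- **SAP 9.6.7.** "subjects who develop anti-etelcalcetide antibodies at any time, at baseline and post baseline will be tabulated for the etelcalcetide arm". That is three counts: at any time, at baseline and post baseline.

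**The concern.** Two places rely on a baseline antibody sample, and the only schedule that sites have does not appear to provide one. A pre-dose sample that was not drawn cannot be obtained afterwards.

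Without it, the baseline count in SAP 9.6.7 would be empty. A subject who was reactive before the first dose would look the same as one who became positive on etelcalcetide, so the endpoint could not be reported as formation. The baseline hepatitis test in 7.4.1 would lose its source as well, because no other baseline sample is stored for that purpose.

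**Working it through.** The plan states no figure for this point. The check is a reading of the schedule, a test of how far that reading can be trusted, and the arithmetic of the three counts.

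**1. Column position.** The visit columns of Table 2 are Screening, Day 1, then Weeks 2 to 17. The first ADA mark is in the third visit column (Week 2, study days 8 to 14) and the second in the thirteenth (Week 12). The row directly above, 25(OH)D, has its single mark on Day 1.

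**2. Exposure before a Week 2 draw.** Assessments are to fall on the same dialysis weekday as the first dose, where possible. With three doses a week, 3 × 1 week = 3 scheduled IV doses precede the Week 2 draw. Protocol 7.4 has bloods taken before IP, but that protects only against the dose of the same session. Under SAP 5.2, baseline for laboratory values other than PTH, cCa and phosphorus is the last value on or before Study Day 1. By that rule a Week 2 sample cannot serve as baseline.

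**3. Reliability of the column reading.** Some rows of the current Table 2 can be compared with the protocol text:

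| Row | Table 2 as extracted | Text | Shift |
|---|---|---|---|
| Titration, 1st mark | Week 5 | Week 5 (6.2.1.2) | none |
| Titration, 3rd mark | Week 14 | Week 13 (6.2.1.2) | right |
| Predialysis PK, 1st mark | Week 4 | Week 4 (7.4.2) | none |
| Predialysis PK, 2nd mark | Week 13 | Week 12 (7.4.2) | right |
| Pill count, 1st mark | Week 2 | Week 3 (7.3.11) | left |

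A true Day 1 ADA mark would have had to move right to appear at Week 2. The rightward shifts seen are in late columns. Among the early marks, the titration and PK rows are in place and pill count has moved left. In the replacement table printed in the Amendment 3 summary, the first oral dispensing mark also sits too far left, under Screening. The two copies of Table 2 in that summary, used here only as evidence on alignment, both put the first ADA mark at Week 2. Their second ADA mark differs (Week 13 and Week 12). Week 2 is therefore the better reading of the first mark, but Day 1 cannot be ruled out.

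**4. What the three counts give.** Let B be the subjects positive at baseline, P those positive post baseline, and A those positive at any time.

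- With a baseline sample: A = B ∪ P, so A − B is the number positive after baseline and not positive at baseline.
- Without one: B is unobserved and A = P. Subjects already reactive before dosing who stay positive are inside P and cannot be removed.

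**5. Size, by assumption.** The planned etelcalcetide arm is about 330. The number who could not be classified is 330 × the pre-existing rate, if all of them are sampled and remain positive:

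- 0.5%: 330 × 0.005 = 1.65, about 2
- 1%: 3.3, about 3
- 2%: 6.6, about 7
- 5%: 16.5, about 17
- 10%: 33

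**The case against.** The strongest reply is that the contrary evidence is one tab position in a table with demonstrable one-column errors, while the readable prose points to a pre-dose sample. Protocol 7.4.1 names one, SAP 9.6.7 tabulates it, baseline assessments belong to Day 1, and section 7.2.3 says "The IP is to be administered after all pre-dose assessments have been completed on day 1". This has real weight. It shows that the sponsor very probably intended a baseline sample, and it is why the original layout must be checked. It does not remove the conflict: the general Day 1 wording names no test, section 7.5 is silent on timing, and the checkable early marks give no support for a rightward shift.

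A reader might also infer that SAP 9.6.7 itself would report pre-existing antibodies as formed on treatment. If formation were 2% and pre-existing reactivity 1% to 5%, the any-time count would read 3% to 7%, or 1.5 to 3.5 times the formation rate. The documents do not support that. The same sentence plans the baseline count, and subtraction recovers the formation rate exactly: 3% − 1% = 2% and 7% − 5% = 2%. The overstatement arises only if one planned count is ignored. What remains against the SAP is wording, since it applies the verb for developing antibodies even to the baseline count.

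Finally, exclusion criterion 202 bars earlier trial exposure to etelcalcetide, which may make pre-existing reactivity less common. It does not show that there is none, and the SAP plans a baseline count all the same.

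**Conclusion.** The point holds as a conflict between the schedule and the passages that depend on it, with medium confidence because it rests on the extracted layout of Table 2. If the original shows the first ADA mark on Day 1, Table 2 agrees with 7.4.1 and SAP 9.6.7, and only the silence of section 7.5 remains.

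If the original shows Week 2 and sites follow it, the baseline count cannot be produced and pre-existing antibodies cannot be separated from induced ones. That would affect about 2 to 33 of 330 subjects over an assumed pre-existing rate of 0.5% to 10%; the documents give no rate. It would be too strong to say that no baseline sample was planned, or that pre-existing antibodies will be counted as formed.

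**What to change.** 1. Check Table 2 in the original protocol.
2. State a pre-dose Day 1 ADA draw in both Table 2 and section 7.5, so that they agree with section 7.4.1 and SAP 9.6.7. Say whether the Week 2 mark is a separate on-treatment sample or was meant to be this one.
3. Optionally, have SAP 9.6.7 print the number with a negative result, or no result, at baseline and a positive result afterwards. With a baseline sample the planned counts already yield it, so this only saves the reader a subtraction.

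The cost is one schedule mark at a visit that already draws blood for PTH, albumin and calcium, phosphorus and 25(OH)D, plus a sentence in section 7.5. The downside is that subjects without a baseline sample must be shown separately. They include those with known HIV, whom section 7.5 exempts from antibody sampling. If sampling is already complete, the schedule cannot be repaired; the report should then state how many subjects have a pre-dose ADA result and show the others as unclassifiable.
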